Cover Page for ClinicalTrials.gov

Document:

Protocol and Statistical Analysis Plan

Official Study Title:

Dulce Digital-Me: An Adaptive mHealth Intervention for Underserved Hispanics with Diabetes

NCT#

NCT03130699

Document Date

May 30, 2017

Dulce Digital-Me Protocol

The proposed randomized controlled clinical trial will enroll 414 participants according to the inclusion and exclusion criteria listed below to compare the effectiveness of Dulce Digital (DD) and Dulce Digital-Me (DD-Me) in improving participants' clinical control (HbA1c-primary, LDL-c, and SBP), adherence, and patient-provider communication in underserved Hispanics with poorly controlled type 2 diabetes mellitus (T2DM) across 12 months. The protocol was developed in accordance with Good Clinical Practice, SPIRIT, and CONSORT 2013 guidelines.

The primary aim of this study is to compare the effectiveness of DD-Me versus DD in improving diabetes clinical control [HbA1c-primary, low-density lipoprotein cholesterol (LDL-c), and systolic blood pressure (SBP)] over 12 months. The secondary aims are to compare the effectiveness of DD-Me versus Dulce Digital in improving patient adherence and patient-provider communication over 12 months, and to examine the cost-effectiveness of DD-Me versus DD. An exploratory aim will examine whether effectiveness, cost and/or acceptability differ significantly between DD-Me adaptive feedback methods [i.e., automated messaging versus telephonic MA Health Coach-delivery].

1. INCLUSION/EXCLUSION CRITERIA

Inclusion Criteria:

- Self-identified as Latino/Hispanic
- Age 18 or older
- Registered patient of the collaborating Federally Qualified Health Center (FQHC)
- Diagnosed with T2DM (Type 2 Diabetes Mellitus)
- HbA1c \geq 8.0% and/or SBP \geq 140 and/or LDL-c \geq 100 mg/dL within 90 days of enrollment

Exclusion Criteria:

- Severe illness precluding regular clinic visits
- Pregnant or lactating
- Type 1 or gestational diabetes
- Lack of minimal literacy
- Plans to relocate
- Severe auditory or visual problems
- Primary language other than Spanish or English
- Not willing to carry a mobile phone

Individuals who meet inclusion criteria (and do not meet exclusion criteria) will be randomized to the Dulce Digital or DD-Me intervention condition.

2. SETTING AND SCREENING

The trial will be conducted at, a Federally Qualified Health Center (FQHC) that serves a low-income, largely Hispanic population of over 66,500 patients in San Diego County. A business agreement between Scripps Health and the FQHC will be established and approved by Scripps Health legal department.

Patient census data retrieved in preparing the current proposal support the feasibility of the proposed timeline and target sample. Electronic health records (EHR) will be used to identify potentially eligible patients who will be contacted by specially trained, bilingual research assistants. The support of the FQHC administrative leadership, staff, and utilization of EHRs for recruitment, our experience in recruiting patient samples from community settings, and the large number of potentially eligible patients will maximize our ability to recruit the sample in a timely manner. Recruitment and screening at all stages and for all study components will use IRB approved scripts and data collection forms. Established standards of practice for clinical research will be followed for consenting and enrollment of participants. A screening database will be developed and maintained throughout the trial. All information necessary for clinical trials reporting will occur in accordance with (NIH) CONSORT guidelines.

3. RECRUITMENT

Referrals to the trial will be made through review of EHR, which compiles all patients meeting criteria according to demographics and clinical indicators. Guidance on participant recruitment will be provided by clinic physicians. Potentially eligible participants will be contacted on behalf of the clinic by trained, bi-lingual research staff, who will describe the study, and review eligibility and interest.

4. WRITTEN INFORMED CONSENT; ENROLLMENT AND RANDOMIZATION

Written Informed Consent and Enrollment:

Patients who are eligible and interested will be invited to an in-person, group-based, "Initial Visit," at which the study will be fully described, written informed consent will be obtained (Informed Consent document uploaded with this initial Study Application), and baseline self-report and clinical assessments will be performed. Approximate duration for this visit is 3 hours.

Randomization:

The study will apply a block randomization scheme, which will be computer-generated by the trial statistical consultant and administered by designated research staff. The study statistician will place assignments into sealed envelopes labeled with participant ID numbers. At the conclusion of the Initial Visit, the Project Manager will unveil group assignment. Laboratory staff who perform the clinical assays (primary study outcomes), data analysts, and research staff (with the exception of the Project Manager who will conduct randomization) will be blinded to group assignment.

At the conclusion of the Initial Visit, participants will be randomized to DD or DD-Me, delivered through automated text message, or telephonic communication, meet study staff (nurse, medical assistant [MA]), and receive training on intervention devices. All participants will continue to receive standard care at the clinic. Month-6 and month-12 assessments will be conducted at the same site. DD and DD-Me will be delivered between baseline and month-6 assessments, and are both intended to enhance the self-management support component of the Chronic Care Model (CCM).

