7. ASSESSMENTS AND DATA COLLECTION

Clinical Measures:

- Clinical specimens (blood draws), HbA1C and lipid assays
- Physical measures (blood pressure, weight, height)

As part of Aim 1, we will evaluate key clinical indicators of diabetes control by measuring HbA1c, lipids, and BP. At baseline, month-6, and month-12 assessments, blood will be drawn at the clinic by existing Neighborhood Healthcare laboratory staff following a 12-hour fast and processed by Quest Diagnostics Inc., which adheres to all guidelines set forth by the College of American Pathologists. The primary outcome of HbA1c will be assayed by Immunoturbidimetry (Integra 800, Roche). Research assistants will measure BP and anthropometrics using standardized protocols and instrumentation.

Self-Reported Measures and EHR Data Extraction:

- Participant responses to survey instruments
- Records of demographics, comorbidities, and medications extracted from EHRs;

For Aim 2, participants will complete self-report measures of patient-provider communication, and adherence to medication and other diabetes self-management behaviors (dietary intake, physical activity, blood glucose monitoring) at all 3 time-points. Via self-report we will also assess demographic

and health related factors (including medication use) for screening and sample description purposes, and the fit of the overall theoretical model. Patient EHRs will also be reviewed for patient information (i.e., demographics, comorbidities, and medications).

Patient Focus Groups:

As part of the Process Evaluation, 20 participants from the DD-Me condition [split evenly between automated messaging (n=10) and MA-delivered (n=10)] will be invited to key informant interviews to share their experiences with the intervention. Focus group participants must be willing to provide informed consent; available for scheduled focus group/s; and speak Spanish or English. We will not conduct focus groups with Dulce Digital participants as a process evaluation has already been conducted as part of our original RCT.

Electronic health records abstraction:

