8. DATA TRACKING

All data are tracked in a Research Electronic Data Capture (REDCap) database and reviewed on a regular basis by supervising research staff. Intervention fidelity forms are used to track the frequency, duration, and content of all telephone outreach to participants, including blood glucose triage and “no (EMA, blood glucose, or Wisepill) data” calls for all participants; and weekly MA Health Coach feedback calls for the DD-Me telephonic Health Coach group. The CYCORE system actively tracks the content and date/time of delivery or receipt of outgoing core content, EMA items, and feedback messages, as well as participants’ responses to EMA items. CYCORE reports are reviewed on a regular basis to ensure that intervention content is delivered as designed; any deviations from protocol or temporary system outages are tracked in REDCap.

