9. CONFIDENTIALITY AND DATA ACCESSIBILITY

Confidentiality will be protected by identifying all data forms with a participant ID number, which will be linked to participant identifiable information only on a master list, stored in password protected form on a password protected computer at both primary performance sites, separate from any other study data, and available only to the study PIs, project managers, and other trained research personnel working under the PIs’ supervision if necessary for participant contact, tracking, or follow-up purposes. In general, the trial will take every possible precaution to protect data and ensure that confidentiality is protected both within and across performance sites, via use of ID numbers, safe transport, and other IRB approved procedures. All procedures will be discussed with clinic staff prior to implementation and will be reviewed and approved by the Scripps, SDSU, and UC San Diego IRBs.

Access to individually identifiable private information about the participants will be available only to MPIs [name] and [name] and trained research staff (e.g., project managers) working under their supervision who require this information for a specific purpose. All participant information and data will be de-identified (identified by participant number only). In all cases where data transfer between sites is required, data will be directly transferred from site to site (without stops, excepting emergency) and will be transported in de-identified form, separated from consent forms or other identifying information, and carried in a locked storage box.

8. RETENTION STRATEGIES.

The research team has gained substantial experience with approaches to minimizing attrition through previous efforts. These lessons learned will be applied to maintain the cohort in the proposed study. All participants will receive cohort maintenance postcards at interim study points and reminder postcards prior to each assessment appointment, and will be contacted and rescheduled if an appointment is missed.

Participant Compensation:

Monetary compensation (\$50, \$25, \$40 gift cards for baseline/initial visit, month-6 and month-12, respectively) for time and effort rendered will be offered to all participants following each assessment visit.

Staff Skill:

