9. STUDY OVERSIGHT

Collaborating Sites and Plan:

Performance sites include Scripps Whittier Diabetes Institute (SWDI) of Scripps Health (MPI [name]), SDSU (MPI [name]), and UC San Diego (Co-Investigator [name]). In addition, patient recruitment, assessment, and intervention activities will take place at a collaborating FQHC. The study investigators will work with clinic leadership, providers, and staff to optimize plans for patient identification, data collection, and study implementation, including collaboration in developing safety and protocols and staff training. Twice monthly research meetings (or more often as needed) involving the study PIs and all central study staff across both sites will maintain consistent processes and communication. All research staff will be centrally trained and supervised by the study PIs.

Oversight of Clinical Outcomes and Intervention:

SWDI will have primary oversight for Aim 1 (clinical outcomes), cohort identification process via EHR, and interventionist (nurse, MA) training and support, and will also act as the primary liaison to the clinic sites and stakeholders groups. A Project Manager will be housed at Scripps to oversee patient identification, EHR and (overall) implementation of the intervention and staff trainings.

Oversight of Self-Reported Outcomes:

SDSU (with appropriate registration volunteer staff as required) will have primary oversight for the patient reported outcomes Aim (2). MPI [name] (SDSU) will also oversee the overall program evaluation, in close collaboration with Co-I [name] (Scripps), including conducting patient focus groups and obtaining nurse, MA, and other provider input regarding the intervention, and database development, data entry, data verification, and overseeing data analysis in collaboration with the study statistician. A Project Manager will be employed at SDSU to oversee and contribute to the patient reported assessment outcome and overall program evaluation.

Oversight of CYCORE System:

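### Blinding is claimed for data analysts and research staff with one exception, but the plan's own division of roles does not deliver it

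*Combined protocol and SAP*

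**What the plan says.** Protocol section 4, under Randomization, states that laboratory staff who run the assays are blinded and continues that "data analysts, and research staff (with the exception of the Project Manager who will conduct randomization) will be blinded to group assignment". No other exception is given. The same paragraph says the block scheme is "computer-generated by the trial statistical consultant and administered by designated research staff", and then: "The study statistician will place assignments into sealed envelopes labeled with participant ID numbers".

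Other parts of the document assign these roles and data flows:

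- Section 9, Study Oversight (self-reported outcomes): one of the principal investigators is responsible for "overseeing data analysis in collaboration with the study statistician".
- Section 9, Confidentiality and Data Accessibility: "All participant information and data will be de-identified (identified by participant number only".
- Section 4 introduces the nurse and the MA as study staff. Section 5b has a trained MA deliver the adaptive feedback to half of the DD-Me participants.
- Section 8, Data Tracking: "Intervention fidelity forms are used to track the frequency, duration, and content of all telephone outreach to participants". These include "weekly MA Health Coach feedback calls for the DD-Me telephonic Health Coach group". REDCap holds all data, and supervisory research staff review it regularly.
- Section 7, Assessments and Data Collection: "Research assistants will measure BP and anthropometrics using standardized protocols and instrumentation".

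**The concern.** A blinding statement with a single named exception is a strong claim, and readers of the trial report will rely on it. Here other text assigns knowledge of allocation to people whom the statement treats as blinded, or does not mention.

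This matters because the plan leaves choices to be made once data are in hand. The SAP's Analytic Plan adds covariates after testing baseline balance, and has outliers examined without a rule for handling them. The EHR abstraction part of section 7 fills in missed visits with routine-care values from an assessment window that is not defined. Analyst blinding is the usual protection for such choices, and they can reach HbA1c even though its assay is protected. Systolic pressure, which is part of the primary aim, is measured by staff, so it depends on the measurer not knowing the arm.

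**Working it through.** No arithmetic applies. The point does not touch N = 414, alpha of .05 or power of .80. The check is to set the statements side by side.

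1. **The statistician and the ID-to-arm link.** Section 4 has the study statistician match assignments to participant IDs. The confidentiality section says study data carry the participant number, so the label on the envelope and the key in the dataset are the same kind of identifier. Whoever fills the envelopes can, in principle, join arm to outcome.

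2. **The statistician and the analysis.** Section 9 has the same named role collaborate in overseeing the analysis. Taken with step 1, a person with a hand in the analysis has seen individual allocations. The only exemption in section 4 is the Project Manager, so this role is not covered. No section describes masked codes, an independent envelope preparer or a separate blinded analyst.

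3. **Intervention staff.** An MA who gives the feedback in the telephonic arm knows that those participants are in it. If the MA counts as research staff, the single-exception wording fails on this ground alone. If not, the plan should say so.

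4. **Who is exempt.** The oversight section describes a Project Manager at Scripps, another at SDSU and a third coordinating CYCORE. Section 4 does not say which one randomizes. The SDSU manager contributes to assessment of patient-reported outcomes, so the answer affects those outcomes. Section 4 also has designated research staff administer the scheme, without saying whether this means only the Project Manager.

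5. **Fidelity records.** Triage and missing-data calls are logged for everyone, but weekly coaching calls occur in one arm only. A log of such calls therefore reveals the arm. The stated reviewers are supervisory staff, while blood pressure is taken by research assistants. Nothing says whether research assistants can open the records, and nothing prevents it.

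Steps 1 to 3 show that the claim is not delivered as written, step 3 on the condition stated there. Steps 4 and 5 are gaps in the description, not demonstrated breaches.

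**The case against.** The strongest reply is that several links are inferred. The documents do not list the study statistician among the blinded data analysts, do not say that this person fits the models, and do not say that a copy of the list is kept once the envelopes are filled. A separate blinded analyst is not excluded. That is fair, and it limits the point: the text shows access to allocation by someone who collaborates in overseeing the analysis, not that the models will be run unblinded.

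Three stronger readings are tempting and are not supported:

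- A reader might infer that the fidelity forms carry an arm label. No such field is described. They reveal one arm through the calls they record.
- A reader might infer that blood pressure readings will be biased, and attach a size to the bias. No section says that assessors see these records; the supervisory reviewer could be the exempt Project Manager. The documents give neither a bias nor a standard deviation for systolic pressure from which to build a figure.
- A reader might assume that the trial statistical consultant and the study statistician are different people, so that moving the envelopes to the consultant settles the matter. The two titles stand in adjacent sentences and nothing says whether they are one person or two.

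It can also be said that covariates are triggered by baseline imbalance and not by outcome results, that EHR values are at least confined to a window, and that pre-specification would close these gaps whoever is blinded. This is true, but the plan has not pre-specified them. Masking and pre-specification are complementary.

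**Conclusion.** The blinding statement is wrong as written. Two roles outside its only exception have access to allocation: the study statistician, who prepares ID-labelled assignments and collaborates in overseeing the analysis, and the MA, if counted as research staff. The fidelity records are a further possible route whose reach the documents leave open.

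The expected impact is small. HbA1c is assayed by laboratory staff stated to be blinded, so for the primary outcome the exposure runs only through open analysis choices and EHR substitution. Systolic pressure and self-report outcomes are more exposed, but only if assessors can learn the arm, which the documents neither state nor rule out. No numerical size can be given. The conclusion rests on reading the study statistician in sections 4 and 9 as the same role, which the shared title supports.

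**What to change.** Four changes, none of which needs new staff:

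- Have a person with no role in the analysis fill the envelopes and hold the ID-to-arm list. This can be the statistical consultant if that is a different person from the study statistician. If not, use an existing staff member with no part in outcome assessment or analysis.
- Give the study statistician and the analysts masked group codes until covariates, outlier handling and EHR substitutions are fixed in writing and the database is locked. Use three codes, not two: the planned groups are equal at 414 / 3 = 138, whereas pooling the DD-Me arms gives 2 × 138 = 276 against 138, and the sizes would give the code away.
- Set permissions so that those who measure blood pressure or collect the month-6 and month-12 surveys cannot open fidelity records or CYCORE feedback records.
- Restate the claim as covering laboratory staff, outcome assessors and analysts, and name which Project Manager and which intervention staff are unblinded.

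The cost is one reassigned task and some database settings. The downside is that the person preparing envelopes must be available throughout enrolment. Sample size, power and delivery of the interventions do not change.

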5. INTERVENTION

5.a. Dulce Digital:

Practical barriers (e.g., work, caregiving, transportation) limit the reach of traditional or face-to-face DSME programs for underserved, at-risk patients. mHealth technologies have the potential to circumvent some of these obstacles. Recently we developed Dulce Digital (DD), which included culturally-tailored and health literacy-sensitive educational and supportive text messages [i.e., short message service (SMS)], combined with patient monitoring and transmission of blood glucose values. Dulce Digital participants received text messages derived from the Project Dulce DSME curriculum, medication reminders, and blood glucose monitoring prompts. As a “static” intervention, all Dulce Digital participants received the same content and dosage of messages (2-3 messages daily initially, with frequency tapered over 6 months). A care-team nurse monitored transmitted glucose values, assessed possible reasons for high-risk values, and encouraged follow up with the primary care provider as needed. In a recent RCT of N=126 Hispanic patients with poorly controlled T2DM ($\text{HbA1c} \geq 8\%$), Dulce Digital led to improved glycemic control across 6 months, relative to usual care [HbA1c mean $\Delta = -1.0\%$ vs. -0.2% , $p<.05$]. Our process evaluation indicated that DD was both feasible and acceptable; however, patients expressed a preference for intervention content tailored to their individual self-management needs and behavioral progress (i.e., an “adaptive” intervention).

Participants in this group receive the original DD, culturally and health literacy-appropriate text messages between baseline and six months (“Core Content”). Over this same period, participants are encouraged to regularly check glucose using a cellular-enabled monitor (“Remote Glucose Monitoring”), manage their oral medication(s) monitor their medication taking using the cellular-enabled pillbox (“Remote Medication Adherence Monitoring”) and respond to ecological momentary assessment (“EMA”) questions about health behaviors and well-being via text message.

5b. Dulce Digital Me (DD-Me):

To accommodate patient and provider feedback and consistent with research asserting the value of adaptive interventions, Dulce Digital Me (DD-Me) will include the DD components described above plus adaptive behavioral feedback/goal-setting. The adaptive behavioral feedback and goal-setting component will be facilitated by the CYCORE system (developed and maintained by UCSD – a subcontracted institution on this grant), and will be informed by participants’ real-time, wirelessly-transmitted ecological momentary assessment (EMA) and medication adherence data. The feedback/goal-setting specific to DD-Me will be delivered electronically using a computer-generated algorithm in 50% of the DD-Me sample, and by a specially trained, bilingual medical assistant (MA) in the other 50% to evaluate difference in delivery mode.

